# Proof of Mechanism Evaluations

The following will be investigated to evaluate proof of mechanism:

- Expression of C7 as determined by immunofluorescence (IF).
- The presence of mature anchoring fibrils as determined by immunoelectron microscopy (IEM).
- The change in the treated target and control wounds area from baseline (Day 0) based on investigator assessment of wound healing.

CONFIDENTIAL Page 11 of 75

Final Version 8.0, 29 Oct 2019

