### 2.2.2 Secondary

- 1) To evaluate mechanism of action of FCX-007 at visits 5 (Week 4), 6 (Week 12), 8 (Week 25), 10 (Week 52), and unscheduled visits through the evaluation of skin biopsies for C7 expression and the presence of anchoring fibrils.
- 2) To evaluate the efficacy of FCX-007 through an intra-subject paired analysis of target wound area at visits 5 (Week 4), 6 (Week 12), 8 (Week 25), 10 (Week 52), and unscheduled visits, comparing FCX-007 treated wounds to untreated wounds through investigator assessment of wound healing based on the digital images of wounds.

[figure not shown]
CONFIDENTIAL Page 16 of 75

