Proceeding to administration of FCX-007 after a stagger requires that the previous subject complete Week 4 evaluations and the Investigator must have received approval from the Data Safety Monitoring Board (DSMB) to continue the study prior to the next subject's FCX-007 administration.

At a minimum, FDA and DSMB approvals are required for enrollment of pediatric subjects. Local oversight committees may also require approval.

Each phase of the study is divided into four (4) periods: Screening, Wound Monitoring, Treatment, and Long-Term Follow-Up. The Screening Period consists of entry criteria evaluations, the collection of one set of three 3-4 mm biopsies for FCX-007 manufacturing, and the identification and photography of potential target wounds. FCX-007 manufacturing requires about 4 months. This period is the Wound Monitoring Period. Subject target wounds may be imaged a minimum of two times (at least 4 weeks apart) during this period. The purpose of the imaging is to identify wounds with the most consistent wound areas that meet criteria, and to establish a baseline area that takes into account natural wound area variation. The Wound Monitoring Period is expected to have a duration of approximately four months; however, this period can extend beyond four months to accommodate patient scheduling, variations in manufacturing duration and protocol mandated delays (i.e. pauses due to staggered treatment).

After FCX-007 manufacturing is complete, Fibrocell (the Sponsor) and the Investigator will mutually agree on the date of receipt of FCX-007. The duration of the Treatment Period may fluctuate between two and four days. The Treatment Period visits (Day -2 to Day 2) will be scheduled so that the day of dosing (Day 0) is the day of receipt of FCX-007. Prior to dosing, wounds are identified that meet treatment criteria based on imaging results obtained. Up to three pairs of target wounds may be identified for each subject and the Investigator will pair the target wounds according to similarity in wound area.

One wound in each pair will receive FCX-007 and the other wound no treatment.

Safety and proof of mechanism evaluations are conducted during site visits at Visits 5, 6, 8 and 10 (weeks 4, 12, 25, 52), and unscheduled visits. Proof of mechanism will be monitored through assays conducted on biopsies taken from target wounds and areas of intact skin in which FCX-007 was administered.

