#### 9.3.1 Investigator Assessment of Wound Healing

The investigator will assess wound healing of target wounds (treated and control/untreated) based on the digital images of the target wounds. The investigator will assess wound healing of target wounds from 0% to 100% healed on a categorical scale. The wound healing assessment will be captured in the following categories.

- 0%
- 1-9%
- 10-24%
- 25-49%
- 50-74%
- 75-89%
- 90-99%
- 100%

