#### 13.2.1 Post-FCX-007 Administration Adverse Event Monitoring

The Investigator must monitor the subject's wounds closely for additional blister formation and expansion of the border of the wound during injections and immediately post-administration up to the 2 day follow up visit. Additional blister formation and/or expansion of the border of the wound must be recorded as an adverse event.

CONFIDENTIAL Page 57 of 75

Fibrocell Technologies RDEB Phase I/II Protocol Final Version 8.0, 29 Oct 2019

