#### 14.6.3 Target Wound Area

Dimensions of target wounds (treated and control)/ partial wounds will be obtained using the Canfield VECTRA H1-270 System. Dimensions obtained will include length, width, and area (in cm^2). Change in area and other dimensions from baseline initial target wound identification and between visits will be evaluated.

The healed skin area of the target wounds (treated and control)/ partial wound will be evaluated using photographs by the investigator at each post-treatment visit and by treatment and study phase, and will be compared between treatments for each study phase.

The percent of change in the target wound (treated and control) / partial wound area from baseline will be assessed by the investigator at each post-treatment visit and by treatment and study phase, and will be compared between treatments for each study phase.

The proportion of target wounds (treated and control) / partial wounds achieving complete wound closure (≥ 90%) will be reported at each post-treatment visit by treatment and study phase and compared between treatments for each study phase.

These analyses will be performed for both FAS and PP populations.

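### The investigator healing scale behind secondary objective 2 has no category for an enlarged wound, and Section 14.6.3 names no treated-versus-control comparison of signed wound area

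*Combined protocol and SAP*

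**What the plan says.** Section 2.2.2 sets the only efficacy objective as an intra-subject paired analysis, "comparing FCX-007 treated wounds to untreated wounds through investigator assessment of wound healing based on the digital images of wounds". Section 9.3.1 defines the rating: "The investigator will assess wound healing of target wounds from 0% to 100% healed on a categorical scale". Its eight categories are 0%, 1-9%, 10-24%, 25-49%, 50-74%, 75-89%, 90-99% and 100%. Section 14.6.3.1 repeats them. Neither section gives a category or rule for a wound larger than at baseline. Table 2 schedules the rating from Visit 5 (Week 4) to Visit 10 (Week 52).

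Section 14.6.3 describes four analyses of the wounds:

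- **Imaged dimensions**, including area in cm²: "Change in area and other dimensions from baseline initial target wound identification and between visits will be evaluated". No comparison between treatments is named here.
- **Healed area**, judged by the investigator from photographs and compared between treatments.
- **Percent change in area**, compared between treatments: "The percent of change in the target wound (treated and control) / partial wound area from baseline will be assessed by the investigator".
- **Closure**, the proportion of wounds "achieving complete wound closure (≥ 90"%), compared between treatments.

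The synopsis, under Proof of Mechanism Evaluations, links area change to the rating: "The change in the treated target and control wounds area from baseline (Day 0) based on investigator assessment of wound healing".

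**The concern.** Wound area in this disease can move in both directions. Section 3.1 says that wound monitoring is meant "to establish a baseline area that takes into account natural wound area variation", and Section 13.2.1 provides for growth after injection: "Additional blister formation and/or expansion of the border of the wound must be recorded as an adverse event". A scale that starts at 0% can show only improvement.

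Two results would be understated if wounds enlarge. If untreated wounds grow while treated ones hold steady, a real benefit shows as little or none. If treated wounds grow while controls hold steady, the efficacy comparison shows little or no harm. The imaging system already measures signed area on both wounds, but the plan does not commit to comparing it between treatments.

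**Working it through.** **Inputs.** The scale comes from Sections 9.3.1 and 14.6.3.1, and the objective from Section 2.2.2. Section 14.1 states that no formal sample size calculation was done. The documents give no SD, effect size or frequency of enlargement, so there is no plan figure to reproduce. Everything numerical below is illustrative.

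**Step 1: single pairs.** Let h be the percent reduction in area from baseline, negative if the wound has grown. Ignoring the width of the bands, the scale records max(h, 0).

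| Treated h | Control h | True difference | Difference on the scale |
|---|---|---|---|
| 0 | −40 | +40 | 0 |
| −40 | 0 | −40 | 0 |
| −40 | −10 | −30 | 0 |
| +20 | −30 | +50 | +20 |

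If both values are zero or above, the floor changes nothing.

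**Step 2: mean differences under assumed distributions.** Assume h is normal with mean μ and SD s, capped at 100. Write Φ and φ for the standard normal distribution function and density.

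- Floored mean = μΦ(μ/s) + sφ(μ/s) − c
- Mean with negative values kept = μ − c
- Cap term: c = (μ − 100)Φ((μ − 100)/s) + sφ((μ − 100)/s)

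With s = 40:

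- μ = +30: 30 × 0.7734 + 40 × 0.3011 − 0.65 = 34.60
- μ = 0: 40 × 0.3989 − 0.08 = 15.88
- μ = −30: −30 × 0.2266 + 40 × 0.3011 − 0.01 = 5.24

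Benefit (+30 against 0): 34.60 − 15.88 = 18.7. Harm (−30 against 0): 5.24 − 15.88 = −10.6. Treated stable with controls growing (0 against −30) is the mirror image, +10.6 in place of 29.9.

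| Assumed means (treated, control) | SD | Negative values kept | Floored at 0 | Share kept |
|---|---|---|---|---|
| +30, 0 | 20 | 30.0 | 22.6 | 75% |
| +30, 0 | 40 | 29.4 | 18.7 | 64% |
| +30, 0 | 60 | 27.6 | 15.5 | 56% |
| −30, 0 | 20 | −30.0 | −7.4 | 25% |
| −30, 0 | 40 | −29.9 | −10.6 | 36% |
| −30, 0 | 60 | −29.1 | −11.2 | 38% |

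Over a wider set of assumed means the share kept was 47% to 84% when treated wounds heal on average (+30 or +50), and 16% to 38% when they grow on average (−30 or −50, controls at 0).

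**Step 3: effect on a paired test.** An exact two-sided sign test at 0.05 was simulated with 2,000 runs, 12 independent pairs and SD 40. It used the eight categories, then the same categories with mirrored negative ones. For harm (−50 against 0), tied pairs were 46% on the protocol scale and 9% on the signed scale, and power was 0.33 and 0.54. For benefit (+50 against 0), power was 0.53 and 0.54, so detection hardly changes.

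**Step 4: which planned comparisons are exposed.** The healed-area comparison rests on the investigator's rating and is exposed. Percent change in area is exposed only if it is taken from the same categories. The synopsis suggests that it is; Section 14.6.3 does not say. Closure at 90% or more is not exposed. Imaged area is signed, but its comparison is unnamed and its baseline is initial wound identification, whereas the synopsis uses Day 0.

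**The case against.** Several points on the other side stand.

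- **Harm has other routes.** Safety is the primary objective. Section 13.1.1 makes marked worsening an adverse event and requires blistering near a product-treated wound to be noted as one. Section 13.2.1 covers border expansion. A reader might infer that most harm disappears from the trial; the documents do not support that. The loss is confined to the efficacy rating. These routes still do not replace a paired comparison: the close border monitoring runs only to the 2-day visit, change within normal disease fluctuation is not an adverse event, and Section 14.7.1 does not tabulate events by wound pair.
- **Signed area is not ignored.** Section 14.2 provides summaries by treatment regimen, with change from baseline, and says comparisons should respect pairing. Signed area would therefore be described by treatment. What is missing is a named comparison.
- **Percent change may already be signed.** Section 9.3 has investigators trace the wound perimeter in the imaging software, so an investigator-assessed percent change could be a signed measurement. The text is unclear; it is not shown to be wrong.
- **The magnitudes rest on assumptions.** Normality, the SDs and the mean enlargements are all assumed, and pairs were treated as independent. Where several pairs qualify, Section 9.1 prefers wounds with the most consistent areas, which would reduce fluctuation.
- **Mean scores are not defined.** A reader might infer that an unchanged wound earns a positive average score. The protocol assigns no numbers to these categories, and Section 14.2 plans counts and percentages for categorical data. Any such shift would also affect both wounds of a pair equally under no effect.

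The analyses are exploratory, in up to 12 subjects, and Version 8.0 moved efficacy to the investigator rating deliberately. That argues for adding to the rating, not replacing it.

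**Conclusion.** The point holds in a limited form. The scale named for secondary objective 2 cannot separate an enlarged wound from an unchanged one, so a true treated-versus-control difference is compressed on it when either wound enlarges. Section 14.6.3 does not close the gap, because the signed area has no named between-treatment comparison and the derivation and sign of the percent change are not stated.

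It would go too far to say that the efficacy contrast is distorted in every case. With no enlargement there is no compression, and the closure comparison is untouched.

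The size cannot be fixed from the documents. Under the assumptions above, a 30-point benefit over stable controls appears as 15.5 to 22.6 points, and a 30-point harm as 7.4 to 11.2. The direction is the firmer finding: where wounds do enlarge, average worsening of treated wounds is hidden more than average healing. This is a low-cost improvement to an exploratory analysis and does not invalidate the trial.

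**What to change.** 1. In Sections 9.3.1 and 14.6.3.1, add one category below 0%: *larger than at Day 0*.
2. In Section 14.6.3, add a paired treated-versus-control comparison of signed percent change in imaged wound area from Day 0. Report it alongside the investigator rating, not in place of it. State that percent change in area may be negative, and how the investigator-assessed figure is derived.

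The two parts do different work. The new category separates growth from no change but does not grade it; two enlarged wounds would still tie. The signed area supplies the amount.

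The cost is one CRF change and one extra exploratory analysis, with no new visits or images, since Section 9.3 already has both wounds measured. Reported healing may look slightly less favourable.

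If ratings already made are revisited, re-rate all stored images of both wounds in every pair by the same rule. Re-reading only those rated 0% would be selective, and no masked reader is described. Otherwise leave those ratings as they are and rely on signed area for those visits.

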#### 9.4 FCX-007 Administration

#### 9.4.1 Preparation

A surgical marker will be used to make the following marks:

- Dots at the injection sites around the periphery of the wound at 1 cm intervals
- Two lines, 1 cm apart, perpendicular from the wound margin, indicating the path of injections across the axes.
- Two circles indicating the location of the IF/DIF and IEM biopsies

CONFIDENTIAL Page 43 of 75

[figure not shown]
Fibrocell Technologies RDEB Phase I/II Prote

Final Version 8.0, 29 Oct 2019

**Figure 5** provides a diagram of a target wound with markings. After the markings are in place, the wound will be imaged and biopsies obtained.

Prior to the first administration of IP, small tattoos will be placed on non-blistered skin near target wounds for the purpose of calibrating the images. Topical anesthetic cream will be removed from the treatment area prior to treatment. The treatment area will be cleansed with antiseptic solution.

Figure 5 – Sample Drug Administration Preparation Wound Markings

#### 9.4.2 Administration

Reference Appendix A: Investigational Product Administration Instructions for detailed instructions regarding the administration of investigational product.

Investigational product is administered intradermally at 1 cm intervals around the periphery of target wounds. The intradermal administration must occur up to 1.0 cm of the wound margin and be administered into the mid-to-superficial dermis. Investigators are to administer 0.25 mL per injection. **Figure 6** provides a graphical depiction of an example target wound showing injection sites and biopsy locations. Locations are shown for (A) treatment of an entire wound, and (B) treatment of a region of a large wound.

[figure not shown]
CONFIDENTIAL Page 44 of 75

#### 9.4.2.1 Treatment of Partial Wounds

[figure not shown]
It is preferable to inject whole wounds and not partial wounds; however, partial wounds should be used if whole wounds that meet criteria are not available.

Figure 6 – Example Target Wound, Injection Sites and Biopsy Locations

#### A: Treatment of an Entire Wound

#### **B: Treatment of a Partial Wound**

#### 9.4.3 Visit 5 Administration

Target wounds are administered investigational product up to two times throughout the treatment period; once at Visit 3 (Day 0) and again at Visit 5 (Week 4).

CONFIDENTIAL Page 45 of 75

Final Version 8.0, 29 Oct 2019

## 10 Procedures: Collection and Evaluation of Biopsies

#### 10.1 Collection

Biopsies are collected according to **Table 2 - Schedule of Events**. Biopsy handling and shipping instructions are provided in **Appendix B: Biopsy Collection Procedures**. Unscheduled biopsies or laboratory tests may be performed as necessary to evaluate inflammation, possible SCC growths, or suspected presence of C7/anchoring fibrils (wound healing).

At Visits 5 (Week 4), 6 (Week 12), 8 (Week 25) and 10 (Week 52), up to four (4) and a minimum of three (3) biopsies will be collected:

- Two (2) biopsies from intact skin
  - One for IF and DIF analysis to evaluate
    - C7 expression (IF)
    - C7 antibodies (DIF)
  - One to evaluate C7 mRNA and DNA
- One (1) from the target wound to evaluate C7 mRNA and DNA

At other Visits the Investigator may collect up to six (6) biopsies per visit.

The number and type of biopsies obtained will ultimately depend on the judgment of the Investigator and Sponsor.

#### 10.1.1 Collection Location

At all follow-up visits, biopsies are to be collected as closely to the injection sites as possible. To aid in locating the injection sites, a transparent overlay of the injection sites can be generated from imaging which can be placed over the subject's wound / intact skin. Through use of the transparent overlay, aligned with the wound /intact skin according to the tattoos, biopsy sites are chosen that are in alignment with the injection sites. If more than one pair of wounds is included in the study, the target wound from which a biopsy is obtained may vary from visit to visit, at the discretion of the Investigator, to minimize subject discomfort.

#### 10.1.2 Biopsy Photographs and Markings

Biopsy locations around wounds are to be marked with a small circle. The markings will be photographed prior to collection (reference **Figure 5** for a depiction of biopsy wound markings). Biopsy location and purpose will be recorded in the source documentation.

CONFIDENTIAL Page 46 of 75

Fibrocell Technologies RDEB Phase I/II Protocol Final Version 8.0, 29 Oct 2019

#### 10.2 Evaluation

#### 10.2.1 Immunofluorescence (IF)

Expression of C7 is analyzed at Visits 3 (Day 0), 5 (Week 4), 6 (Week 12), 8 (Week 25) and 10 (Week 52). Skin biopsies may also be obtained at unscheduled visits to evaluate C7 per investigator discretion. A qualified reader will evaluate production of C7.

#### 10.2.2 Immunoelectron Microscopy (IEM)

Expression of C7, both NC1 and NC2 epitopes, and the formation of anchoring fibrils are analyzed through IEM at Visits 3 (Day 0), 8 (Week 25), and 10 (Week 52). Skin biopsies may also be obtained at unscheduled visits. A qualified reader will score the presence of anchoring fibrils. as + (presence of mature anchoring fibrils) or – (absence of mature anchoring fibrils).

#### 10.2.3 DNA Retention and mRNA Expression

At least one skin biopsy is obtained at Visits 5 (Week 4), 6 (Week 12), 8 (Week 25), and 10 (Week 52) to evaluated for genomic retention of C7 proviral vector sequences (DNA retention) as well as mRNA expression.

#### 10.2.4 Autoimmune Assays

C7 Antibodies will be assayed by direct immunofluorescence (DIF) at Visits 3 (Day 0), 5 (Week 4), 6 (Week 12), 8 (Week 25) and 10 (Week 52). Skin biopsies may also be obtained at unscheduled visits per investigator discretion. If there is an autoimmune reaction to C7 then injected fibroblasts may also stain positive for immune reactants. In addition, a Western Blot assay may be performed to complement the indirect and direct IF assays.

The overall assessment of anti-C7 product immune response will be based on each of these assays.

CONFIDENTIAL Page 47 of 75

Final Version 8.0, 29 Oct 2019

## 11 Procedures: Safety Assessments

Timing of safety assessments must be performed in accordance with **Table 2 - Schedule of Events**. Safety assessments include evaluation of medical and medication history, physical / skin examination, vital signs, AEs, and laboratory evaluations. AEs will be captured between visits through use of an Adverse Event Diary. Post-administration changes in these assessments that are deemed to be clinically significant by an Investigator or Sub-Investigator will be assessed as AEs.

## 11.1 Data Safety Monitoring Board

A DSMB comprised of the Medical Monitor, enrolling Pls, and Sponsor representatives and/or designee(s) will hold periodic teleconferences to evaluate the safety and treatment status of all subjects available during the study at these stages:

- After the first subject, prior to the treatment of a second subject in each arm
- After Visit 5 (Week 4) for the third subject, prior to treatment of the first Phase II subject, to make a recommendation as to whether: 1) treatment of adult patients in Phase II of the protocol should continue; and 2) the study should proceed with the enrollment and treatment of children in Phase II of the protocol.
- At any other time as needed

The DSMB has the authority to recommend dose or regimen modifications for safety concerns.

A written summary documenting the results and recommendations of each review will be provided to the investigator(s) and maintained on file with the Sponsor. Additional sub-investigators and scientific personnel may participate in reviews, as appropriate.

The DSMB will provide recommendations about stopping or continuing the trial. To contribute to enhancing the integrity of the trial, the DSMB may also formulate recommendations relating to the selection/recruitment/retention of participants, their management, improving adherence to protocol-specified regimens and retention of participants, and the procedures for data management and quality control.

A DSMB charter will dictate procedures, responsibilities, membership, data requirements and meeting timing.

CONFIDENTIAL Page 48 of 75

Final Version 8.0, 29 Oct 2019

#### 11.1.1 Stopping Criteria

An objective of this study is to generate a safety profile of FCX-007 in subjects with RDEB. Subjects with RDEB have a significantly increased risk of experiencing SAEs such as serious infections relative to the general population; therefore, in most cases, possible discontinuation of the study will be reviewed on a case-by-case basis. Events which will not be reviewed case-by-case that will result in immediate enrollment discontinuation and treatment discontinuation for all subjects are a positive RCL assay and histologically confirmed cancer in combination with the presence of viral vector in the tumor. In addition, the Medical Monitor may interrupt study dosing and/or study entry at any time if medically indicated. To minimize risk, cumulative safety data will be reviewed by the Medical Monitor and DSMB, as outlined in Section 11.1.

Occurrence of any of these observations will trigger a temporary suspension of FCX-007 administration pending a safety investigation:

- A treatment emergent serious adverse event or suspected serious adverse event related to FCX-007, the FCX-007 administration procedure, or any other protocol procedure.
- A positive RCL qPCR assay result. A positive RCL qPCR assay will result in suspension of FCX-007 administration. The result will be confirmed by conducting a biological-based assay. If both assays are positive, FCX-007 administration will be discontinued and no further enrollment into the study will be allowed.
- 3. An autoimmune response determined by the Investigator to be possibly, probably or definitely related to treatment.
- 4. Any systemic infection designated as suspected to be related to FCX-007.
- 5. A treatment emergent uncontrolled bacterial, viral, or fungal infection in a wound that was administered by investigational product where product sterility testing results reported post injection were positive for contamination.
- 6. Any subject diagnosed with a histologically proven skin cancer (including sarcomas) will be biopsied and assayed for viral vector by qPCR. A positive result for viral vector will cause product administration to be suspended.

For subject safety, investigators should continue to follow patients in accordance with study visits and procedures as outlined in the protocol. An occurrence of any of these safety observations will be shared with all study Investigators, DSMB and the appropriate authorities. The DSMB will review the results of the safety investigation and may request any additional data needed to assess the safety of restarting product administration. The DSMB will determine if the suspension can be lifted or if the trial will need to terminate based on their review of the safety investigation.

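### Section 11.1.1 gives two incompatible actions for a vector-positive skin cancer: an automatic, final stop, or a suspension that the DSMB may lift

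*Combined protocol and SAP*

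**What the plan says.** Section 11.1.1 has three parts.

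- **Opening paragraph.** Most possible discontinuations are judged individually, with two exceptions, which "are a positive RCL assay and histologically confirmed cancer in combination with the presence of viral vector in the tumor". It describes this pair as "Events which will not be reviewed case-by-case that will result in immediate enrollment discontinuation and treatment discontinuation for all subjects". It adds that "the Medical Monitor may interrupt study dosing and/or study entry at any time if medically indicated".
- **List of six triggers.** The lead-in reads: "Occurrence of any of these observations will trigger a temporary suspension of FCX-007 administration pending a safety investigation". Item 2 (RCL) begins with a suspension on a positive qPCR, requires a biological-based confirmatory assay, and then states the end point: "If both assays are positive, FCX-007 administration will be discontinued and no further enrollment into the study will be allowed". Item 6 (skin cancer) reads: "Any subject diagnosed with a histologically proven skin cancer (including sarcomas) will be biopsied and assayed for viral vector by qPCR". Its only stated consequence is: "A positive result for viral vector will cause product administration to be suspended".
- **Closing paragraph.** Any of the listed observations goes to the investigators, the DSMB and the authorities. The DSMB reviews the investigation, "may request any additional data needed to assess the safety of restarting product administration", and decides between lifting the suspension and terminating the trial. Item 6 is not excepted.

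**The concern.** A stopping rule has to give one action per event. Here a histologically proven skin cancer carrying the vector meets the condition for an automatic end to treatment and enrolment, and also the condition for a suspension that the DSMB can reverse.

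The event is one of only two that the protocol removes from individual judgement. Safety is the primary objective (Section 2.2.1), and dosing is staggered because the product had not been given to humans before (Section 3.1). Skin cancer is foreseeable in this population: Section 1.1 gives a lifetime risk of aggressive squamous cell carcinoma of over 90% in the severe generalized subtype, and exclusion criterion 5 bars only metastatic disease at the injection site.

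Because of the stagger and roughly 8 months of recruitment (Section 3.4), a tumour in an early subject could be found while later subjects, possibly children in Phase II, still await a dose. The sites, the sponsor and the DSMB would then have text supporting either a final stop or a restart. Under Section 11.1 the DSMB is made up of the Medical Monitor, the enrolling principal investigators and sponsor representatives or designees. With that membership, whether it has any discretion over this event matters.

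**Working it through.** No arithmetic applies. The check compares the trigger, action and decision-maker of each rule in Section 11.1.1 for one event: a histologically proven skin cancer that tests positive for the vector.

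| | Opening paragraph | Item 6 with the closing paragraph |
|---|---|---|
| Trigger | Confirmed cancer of any type, vector in the tumour | Proven skin cancer, including sarcomas, with a positive vector qPCR |
| Treatment | Discontinued for all subjects at once | Suspended, temporarily |
| Enrolment | Discontinued at once | Not addressed |
| Case-by-case review | Excluded | Required (safety investigation, then DSMB) |
| Can dosing restart? | No | Yes, if the DSMB lifts the suspension |

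Three ways of reconciling the two columns were tried.

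1. **Suspend first, stop on confirmation.** This works for RCL, because item 2 writes out both the confirmatory assay and the final action. Item 6 has no second step. When its suspension takes effect, histology is proven and vector has been found. If the tissue is the tumour, both conditions of the opening paragraph are already met, so nothing remains to be confirmed.
2. **Different events.** The opening paragraph covers any cancer and item 6 covers skin cancer, so a vector-positive skin cancer falls under both. Item 6 does not name the tissue assayed. Sections 7.5.1 and 11.4 describe collecting samples of the skin cancer itself to look for vector, which makes the tumour the natural reading.
3. **A precedence rule.** None is stated. The closing paragraph applies to all the listed observations. The Medical Monitor's power to interrupt is discretionary and does not decide which rule governs.

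The other automatic stop, RCL, ends consistently: once both assays are positive, item 2 and the opening paragraph lead to the same action. The only loose end there is that the opening paragraph does not say whether a positive assay means the qPCR screen or the confirmed result.

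Extent: up to 6 + 6 = 12 subjects, or 6 + 7 = 13 if the optional seventh Phase II subject is enrolled (Section 3.3), each with 2 planned administrations, at Day 0 and Week 4.

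**The case against.** The strongest defence is that a specific, mandatory exception normally prevails over a general clause, so the opening paragraph should govern and the list merely describes the first step. Item 2 supports this up to a point: RCL also sits under the temporary-suspension lead-in, and the closing paragraph does not exempt it, yet a confirmed RCL is final. But item 2 is final because it says so. Item 6 does not, and a reader comparing the two could fairly infer that the difference was intended.

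A second defence is that vector is expected in injected skin. Sections 10.1.1 and 10.2.3 provide for biopsies close to the injection sites and for testing of retained vector sequences. A positive biopsy at a treated site might therefore reflect injected fibroblasts beside a tumour, and suspending while that is resolved would be sensible. It would be a coherent two-step rule, but the protocol does not write it.

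Several limits do stand:

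- Dosing halts at once under either rule, a restart would need a positive DSMB decision, and termination remains open to the DSMB.
- On enrolment, item 6 is silent and does not contradict the opening paragraph.
- Each subject's dosing ends at Week 4, so the restart question affects only subjects with a dose outstanding when a positive result arrives.
- The figure of over 90% is a lifetime cancer risk in one subtype and says nothing about how often a tumour would carry vector.
- The DSMB charter, which is not among the documents, may address the event. It could guide conduct but would not remove the conflict in the protocol.

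**Conclusion.** The concern holds, and the section is wrong as written. One of the two automatic stops has conflicting actions. The direct contradiction is whether the event is open to review and whether dosing can resume. Enrolment is a gap: closed under one rule, not mentioned under the other.

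This rests on one reading, that the tissue assayed under item 6 is the tumour; Sections 7.5.1 and 11.4 support it. If other tissue was meant, the section would still need to say so and to state what follows once vector is shown in the tumour. The probability of the event cannot be estimated from the documents. The correction is needed because the rule concerns subject safety in a first-in-human gene therapy trial and cannot be applied unambiguously.

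**What to change.** Make three edits to Section 11.1.1.

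1. Extend item 6 on the model of item 2: a histologically proven skin cancer positive for viral vector ends FCX-007 administration and closes enrolment. Name the tumour as the tissue assayed.
2. In the opening paragraph, specify that the RCL trigger is a qPCR positive confirmed by the biological-based assay.
3. In the closing paragraph, limit the DSMB's power to lift a suspension to the remaining triggers and to RCL qPCR positives that are not confirmed.

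This follows the opening paragraph's mandatory wording. If the sponsor wants item 6 to act as a screen, it should state the confirmation step and the final stop that follows. If it wants DSMB discretion over this event, the opening paragraph must change instead. Some edit is needed in every case.

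The cost is a few sentences and a check that the DSMB charter agrees. Data collection and sample size are unaffected.
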